6.8. Blinding and Breaking the Blind

The clinical study will be performed in a double-blind manner, so the identity of investigational drug and placebo will not be known to investigators, research staff and subjects. At the Clinical Units are to be at minimum two staff members, who are to be unblinded: pharmacist preparing the products to be administered based on randomization list and one person from the team who is to be responsible for verifying the proper preparation of the product doses (quality control). They are not to be involved in any evaluation and examination of the study patients. The unblinded staff members are obligated not to share the randomization list with other staff members during the whole study. The adequate pharmaceutical manual is to be prepared by the clinical units and is to be followed.

The study blind may be broken only in medical emergency (where knowledge of the study drug administered would affect the treatment of the emergency). The decision to break the blind will be made on a case-by-case basis, at the discretion of the Investigator, and if possible, in collaboration with the Sponsor and/or Medical Monitor. If the blind is broken the CRO and Sponsor must be informed as soon as possible. The date, time and reason for unblinding is to be documented in the CRF and in the source data. The applicable standard operating procedure (SOP) will be followed for blind breaking procedures.

After database lock, the overall randomization code will be broken only for reporting purposes.

Suspected unexpected serious adverse reactions (SUSARs), that are subject to expedited reporting, should be unblinded by the Sponsor before submission to the regulatory authority and the Institutional Review Board (IRB)/Independent Ethics Committee (IEC). Information about SUSAR should be sent to all Investigators too (after unblinding the patient).

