8.5. Efficacy Variables

The efficacy will be assessed by using various psychometric scales. Every scale will be performed by experienced and trained raters (certified in PANSS scale) according to planned schedule of assessments.

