8.5.1. Positive and Negative Syndrome Scale

The PANSS is a 30-item scale used to measure symptoms of schizophrenia. The scale has 7 positive symptom items, 7 negative symptom items, and 16 general psychopathology symptom items. Each item is scored on a 7-point scale by the clinical rater based on a clinical interview with the patient.

Positive and Negative Syndrome Scale will be performed at the time points detailed in the Schedule of Assessments (Table 1) and as detailed below:

The efficacy assessment (PANSS) will be performed once at Screening (Day -10 to -2); once at Baseline (Day -1); on Days 1, 7, 14, 21 and 28 when start of ratings is to be within 5 minutes before or after 2h post-dose (it will be performed before any other scale).

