8.5.2. Clinical Global Impression Scale - Severity

The Clinical Global Impression (CGI) Scale is a standardized assessment tool that the Investigator can use to rate the severity of illness, change over time, and efficacy of medication, taking into account the patient's clinical condition and the severity of side effects. The CGI Scale consists of 3 global subscales formatted for use with the Global Scoring Sheet. The first subscale, Severity of Illness, assesses the Investigator's impression of the patient's current illness state; it is often used both before and after treatment. Scores on the Severity of Illness subscale range from 1 = not ill at all to 7 = among the most extremely ill.

Clinical Global Impression Scale - Severity will be performed at the time points detailed in the Schedule of Assessments (Table 1) and as detailed below:

The efficacy assessment (CGI-S) will be performed once at Screening (Days -10 to 2), once at baseline (Day -1); on Days 7, 14, 21 and 28 when start of ratings is to be within 5 minutes before or after 2h post-dose (after PANSS).

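### Protocol 6.8 sends SUSAR information to all Investigators after unblinding, without masking the assignment or shielding the efficacy raters

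*Protocol*

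**What the plan says.** Protocol 6.8 sets the standard that "the identity of investigational drug and placebo will not be known to investigators, research staff and subjects", and SAP 2.3.2 also describes investigators as blinded. The code-break rule in 6.8 is narrow: "The study blind may be broken only in medical emergency (where knowledge of the study drug administered would affect the treatment of the emergency".

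For SUSARs subject to expedited reporting, 6.8 says that they "should be unblinded by the Sponsor before submission to the regulatory authority and the Institutional Review Board (IRB)/Independent Ethics Committee (IEC". The next sentence extends distribution: "Information about SUSAR should be sent to all Investigators too (after unblinding the patient".

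The same section names two unblinded roles at each site, the pharmacist and the person who checks dose preparation, and fences them off: "They are not to be involved in any evaluation and examination of the study patients".

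On who rates, Protocol 8.5 says: "Every scale will be performed by experienced and trained raters (certified in PANSS scale) according to planned schedule of assessments". For PANSS, the source of the primary endpoint, 8.5.1 says: "Each item is scored on a 7-point scale by the clinical rater based on a clinical interview with the patient". For CGI-S, a secondary endpoint, 8.5.2 says that the scale "assesses the Investigator's impression of the patient's current illness state".

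**The concern.** Section 6.8 keeps Investigators blinded, allows a code break only in an emergency, and then routes SUSAR information to every Investigator once the patient has been unblinded, with no instruction to remove the assignment. A safety unit following the text could properly send the arm to every site.

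The efficacy outcomes are clinical judgements, so knowing the arm can influence them. There are two routes:

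- **Direct.** Someone who still has to rate the affected patient learns that patient's arm.
- **Indirect.** A report confirming active drug shows other sites what a recognisable active-arm event looks like and helps them guess the arm of similar patients.

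**Working it through.** The plan states no figure on this point, so the check is mainly a comparison of texts. A short illustration of size follows.

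**Does anything else in the plan repair the sentence?**

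| Place | Content | Repairs it? |
|---|---|---|
| Protocol 6.8, unblinded staff | Bars the pharmacist and dose checker from assessing patients | No. Investigators who receive SUSAR information are not covered |
| Protocol 8.3.1.5 | Names the authority and IEC as recipients; leaves country detail to the Safety Management Plan | No. It does not mention an Investigator copy |
| Protocol 7.1.1.1 and 7.2 | Reasons for withdrawal | No. Unblinding is not listed, so the patient may still be rated |
| SAP 3.3, Table 2 | Major deviations, including violations that could affect PANSS | Doubtful. Disclosure that follows 6.8 is arguably not a violation |

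**Are raters and Investigators the same people?** Section 8.5 assigns every scale to trained raters, and 8.5.2 treats CGI-S as the Investigator's judgement. Together these suggest overlapping roles, at least for CGI-S. For PANSS the protocol names only a clinical rater. SAP 4.7.1 summarises the primary endpoint by rater, so raters are identified in the data, but that neither joins them to nor separates them from Investigators.

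**How many patients directly?** The SUSAR count is an assumption. With 165 planned patients:

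- 1 SUSAR: 1/165 = 0.6%
- 5 SUSARs: 5/165 = 3.0%

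**How much bias?** The inputs n = 50 per group and two-sided α = 0.10 come from Protocol 10.16. With its effect size of 0.5 they give exact t-test power of 0.799, which reproduces the stated 80%. Two further assumptions are not in the documents: k patients in one active arm are unblinded before their Week 4 rating, and each rating shifts by b = 0.5 to 1 SD in the same direction.

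- Bias in the mean difference = k × b / 50, in SD units
- Standard error = √(2/50) = 0.20 SD
- Type I error = 1 − Φ(1.645 − bias/0.20) + Φ(−1.645 − bias/0.20)

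| k | b | Bias (SD) | Bias / SE | Type I error |
|---|---|---|---|---|
| 1 | 0.5 | 0.01 | 0.05 | 0.100 |
| 1 | 1.0 | 0.02 | 0.10 | 0.102 |
| 5 | 0.5 | 0.05 | 0.25 | 0.111 |
| 5 | 1.0 | 0.10 | 0.50 | 0.142 |

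The k = 5 rows are deliberately severe: all five patients are in one active arm, all are rated afterwards, and all shift the same way. The table leaves out the indirect route, for which the documents give no usable figures.

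**The case against.** A reader might infer that 6.8 reveals treatment to the people who rate the primary endpoint. The documents do not support that. PANSS is scored by a certified clinical rater who is not said to be an Investigator, and no section says that raters receive SUSAR notices. This objection stands and limits the point to an unguarded risk.

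The parenthesis in the SUSAR sentence may also give only the sequence of steps. It does not expressly place the assignment in the Investigators' copy, and the Safety Management Plan and code-break SOP, which are not available here, may settle the matter. This stands in part. Disclosure is the natural reading but not the only one. If timing alone was meant, the sentence still does not tell the safety unit what to send.

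The direct effect needs a rating after the notice arrives. Treatment lasts 28 days, and under 7.1.1.1 a patient who stops treatment leaves the trial, with early-termination and follow-up assessments encouraged. Other sites do not rate that patient. This stands and is the main reason to expect little direct bias.

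It would also be tempting to say that widespread indirect unblinding is likely. In the phase 2 trial of another PDE10A inhibitor described in Protocol 2.5, akathisia occurred in 13.3% against 4.9% on placebo and dystonia in 6.0% against 1.2%. Under 5.4.3, exceeding the Table 5 limits on medicines used for such symptoms is recorded as an SAE. But a SUSAR must also be suspected and unexpected, and expectedness rests on the Investigator's Brochure, which is not available. The route is plausible but cannot be sized.

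Finally, 8.3.1.5 refers to European guidance and national requirements that cannot be read here. The point therefore rests on the protocol's internal conflict and not on any outside rule about what Investigators should receive.

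**Conclusion.** The point holds as a low-cost improvement. On its natural reading, the SUSAR sentence in 6.8 releases the treatment assignment to people whom the same section keeps blinded, outside the one exception it allows, and nothing else in the protocol or SAP corrects this. The clearest exposed outcome is CGI-S. Exposure of PANSS raters is possible and unguarded, but not a documented fact.

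The expected direct bias is small. One affected patient moves the type I error of a single comparison from 0.100 to at most 0.102 under the assumed shifts; the extreme five-patient case reaches 0.111 to 0.142. These results depend on an assumed SUSAR count, assumed rating shifts, and ratings taking place after disclosure. The case for change is that the text contradicts itself and is cheap to correct, not that the trial's result is in serious danger.

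**What to change.** Replace the SUSAR distribution sentence in Protocol 6.8 with text stating that:

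1. the Sponsor unblinds SUSARs for the regulatory authority and IRB/IEC;
2. Investigators receive the event information without the treatment assignment, unless the assignment is needed for patient safety;
3. PANSS and CGI raters have no access to unblinded safety reports.

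Record the fact and date of any Investigator or rater unblinding, without the assignment, for the blind data review already planned in SAP 3.3 and 4.2. The data review plan mentioned in SAP 3.3 can carry this. It remains useful if enrolment is already far advanced. Leave the emergency code-break rule unchanged, and align the Safety Management Plan with the revised text.

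The cost is a masked version of the report form and a short amendment, with ethics approval as Protocol 11.7 requires. Investigators still receive the safety information itself.

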6.9. Treatment of Overdose

Standard symptomatic support measures should be used in the case of excessive pharmacological effects or overdose. The patient's conditions will be constantly monitored by Investigator. Each case of overdose will be reported immediately to the Sponsor. The Investigator should follow-up and document the course and the outcome of each overdose even if the subject was withdrawn from the clinical study or if the clinical study has finished and if the patient agrees. Any SAE that occurs due to overdose must be recorded on the Serious Adverse Event Report Form and must be reported by Investigator to the Sponsor within 24 hours of becoming aware of the event.

7. **DISCONTINUATION**

7.1. Study Stopping Rules

The stopping rules described in this section of the clinical study protocol (CSP) are applicable to stopping the study. IMP dosing may be halted temporarily to investigate before the entire study is terminated.

Measures to ensure data integrity and safety of research subjects will be detailed in the Safety Monitoring Plan (SMP) and Data Management Plan (DMP).

If the Investigator, the Medical Monitor or the Sponsor becomes aware of conditions or events that suggest a possible hazard to subjects if the clinical study continues, then the clinical study may be terminated after appropriate consultation among the involved parties. If the investigator considers, that the continuation of the study is a "possible hazard" to the specific subject or the risk-benefit considerations have changed, the Investigator may decide the termination of the study for this subject without the consent/consulting Sponsor. The clinical study may be terminated at the Sponsor's discretion also in the absence of such a finding.

Should the study be terminated, and/or the study centre closed for whatever reason, all documentation pertaining to the study and study drug must be returned to the Sponsor. Any actions of the contract research organization (CRO) required for assessing or maintaining subject safety will continue as required, despite termination of the study by the Sponsor.

7.1.1. Stopping Rules

7.1.1.1. Safety Criteria

After the first dose of IMP, a subject may discontinue from the study for a variety of reasons. Treatment discontinuations may be initiated by a subject or may become medically necessary due to AEs, required treatment with a disallowed medication or therapy, or other reasons, as determined by the Investigator. If a subject discontinues treatment, their participation in the trial will be discontinued. Discontinued subjects should be encouraged to complete all early termination and Follow-up assessments with early termination assessments conducted as soon as possible after the subject is withdrawn.

An individual subject is to be withdrawn from the study if:

• the subject withdraws his/her consent, what he/she is allowed to do at any time and without the need to justify his/her decision,

- the subject requires treatment with any medication known or suspected to interfere with the study medication in the opinion of the Investigator or designee
- the subject is no longer able to participate for other medical reasons (e.g. surgery, adverse event),
- the subject in spite of the earlier evaluation upon recruitment is suspected or found not to comply with eligibility criteria,
- there is evidence or sound suspicion that the subject fails to comply with the protocol directives (compliance with the treatment schedule, non-adherence to dietary rules or other study restrictions that may have influence on study results, non-attendance at study assessments),
- or any other condition occurs which in the opinion of the Investigator no longer justifies or permits a safe participation of the subject.

Each subject has the right to withdraw from the study at any time without prejudice. The Principal Investigator may discontinue any subject's participation when he/she feels it is necessary, for any reason including adverse events or Clinical Study Protocol violation. The subject is to be always informed about the reason for his discontinuation. Reasons for the withdrawal of an individual subject from the study are to be recorded by the Investigator in the Case Report Form and in the Clinical Study Report. In the case of withdrawal caused by adverse drug reaction, the subject is to be under observation until symptoms of the reaction have subsided.

In case of emesis an individual subject is to be withdrawn from the study if:

• the subject suffers from severe emesis within 4 hours after two consecutive days of drug administration. If emesis occurs within 4 hours post-dose and is to be mild or moderate or emesis occurs after 4 hours post-dose, discontinuation of the subject depends on Investigator's judgement and decision.

7.2. Subject Withdrawal and Replacement

In addition to the stopping rules described in Section 7.1.1, a subject will be withdrawn by the Investigator or designee from the study and not be allowed to continue with the study if any of the following criteria are fulfilled:

• If discovered that the subject has entered the study in violation of the inclusion/exclusion criteria stated in the protocol,

• Investigator or the Sponsor stops the study, for any reason (e.g., suspension or discontinuation of study drug development).

While subjects are encouraged to complete all study evaluations, they may withdraw from the study at any time and for any reason. Every effort will be made to determine why any subject withdraws from the study prematurely. All subjects who withdraw from the study with an ongoing AE must be followed until the event is resolved or deemed stable. If a subject withdraws prematurely after dosing, all data to be collected prior to discharge from the clinical site should be collected at the time of premature discontinuation or at the scheduled discharge.

Subject participation may be terminated prior to completing the study and the reason recorded as follows:

- 1. Adverse event,
- 2. Protocol violation,
- 3. Loss to follow-up,
- 4. Subject withdrew consent at own request,
- 5. Other.

A genuine effort must be made to determine the reason(s) why a subject fails to return for the necessary visits or is discontinued from the study. At least 3 documented attempts of telephone contacts must be documented by the site. If the subject is unreachable by telephone, a registered letter, at the minimum, should be sent to the subject requesting him/her to contact the clinic.—In case of failure, patient is considered lost to follow up.

The subject who cannot participate in the study due to not meeting the inclusion or exclusion criteria or is going to withdraw the informed consent before the first IMP administration is to be replaced by the next qualifying alternate.

The subject who withdraws from the study for any reason after any IMP administration or before completion the study, may be replaced by another qualifying alternate only in case if total number of subjects in a given study arm who would complete the study would be insufficient and there are no safety concerns. The subject replacement is defined as recruiting additional patient, but it should be remembered that results from all randomized patients will be analyzed according to the population set definitions described in section 10.1.3.

The replacing subject is to follow the same treatment and protocol procedures as the withdrawn one. The replacing alternate subject is to receive the study products under the same conditions as the withdrawn subjects, and they are to undergo the entire protocol procedure.

8. STUDY ASSESSMENTS AND PROCEDURES

For timing of assessments, refer to the Schedule of Assessments (Table 1).

8.1. Eligibility Screening

For patient eligibility screening assessments and procedures, please refer to Schedule of Assessments (Table 1).

8.2. Medical History, Demographic and Other Baseline Information

The medical history comprises:

- General medical history,
- Medication history,
- Reproductive history.

The following demographic information will be recorded:

- Age,
- Race/ethnicity,
- Height, without shoes (cm),
- Body weight, without shoes (kg),
- Body mass index (BMI) (kg/m²).

Other baseline characteristics will be recorded as follows:

- History of drug abuse,
- History of alcohol abuse,
- Smoking history,
- Special diet (e. g. vegetarian),
- History of blood or plasma donation.

8.3. Safety Variables

8.3.1. Adverse Events

Adverse event reporting will begin for each subject from the date the informed consent form (ICF) is signed and will continue until the final Follow-up Visit.

8.3.1.1. Definitions

8.3.1.1.1. Definition of Adverse Event

Any untoward medical occurrence in a subject administered an IMP and which does not necessarily have a causal relationship with this treatment. An adverse event (AE) can therefore be any unfavourable and unintended sign (including an abnormal laboratory finding), symptom, or disease temporally associated with the use of a medicinal (investigational) product, whether or not related to the medicinal (investigational) product.

Other untoward events occurring in the framework of a clinical study will be recorded as AEs, e.g. those occurring during treatment-free periods (including Screening or post-treatment follow-up periods), in association with study-related procedures and assessments, or under placebo. For study drugs, lack of efficacy may be an expected potential outcome and should not be reported as an AE unless the event is unusual in some way, e.g., greater in severity.

Concomitant illnesses, which existed prior to entry into the clinical study, will not be considered AEs unless they worsen during the Treatment Period. Pre-existing conditions will be recorded as part of the subject's medical history.

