8.3.1.2. Recording of Adverse Events

Adverse events should be collected and recorded for each subject from the date the ICF is signed until the end of their participation in the study, i.e. the subject has discontinued or completed the study.

Adverse events may be volunteered spontaneously by the subject, or discovered by the study staff during physical examinations or by asking an open, non-leading question such as 'How have you been feeling since you were last asked?' All AEs and any required remedial action will be recorded. The nature of AE, date (and time, if known) of AE onset, date (and time, if known) of AE outcome to date, severity and action taken of the AE will be documented together with the Investigator's assessment of the seriousness of the AE and causal relationship to study drug and/or study procedure.

All AEs should be recorded individually in the subject's own words (verbatim) unless, in the opinion of the Investigator, the AEs constitute components of a recognized condition, disease or syndrome. In the latter case, the condition, disease or syndrome should be named rather than each individual symptom. The AEs will subsequently be coded using the Medical Dictionary for Regulatory Activities (MedDRA).

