8.3.1.4. Reporting of Serious Adverse Events

The Investigator will review each SAE and evaluate the intensity and the causal relationship of the event to study drug. All SAEs will be recorded from signing of the ICF until the final Follow-up Visit. Serious AEs occurring after the final Follow-up Visit and coming to the attention of the Investigator must be reported only if there is (in the opinion of the Investigator) reasonable causal relationship with the study drug.

The Investigator is responsible for providing notification to the Sponsor of any SAE, whether deemed IMP-related or not, that a subject experiences during their participation in study within 24 hours of becoming aware of the event.

As a minimum requirement, the initial notification should provide the following information:

- Study number,
- Patient number,
- Sex,
- Date of birth,
- Name of Investigator and full clinical site address,
- Details of SAE,
- Criterion for classification as 'serious',
- Study drug name, or code if unblinded, and treatment start date,
- Date of SAE onset,
- Causality assessment (if sufficient information is available to make this classification).

The Sponsor will request clarification of omitted or discrepant information from the initial notification. The Investigator or an authorized delegate is responsible for sending via email the requested information to the Sponsor within 24 hours of the Sponsor's request.

Initial reports of SAEs must be followed later with detailed descriptions, including clear photocopies of other documents as necessary (e.g. hospital reports, consultant reports, autopsy reports), with the subject's personal identifiers removed. All relevant information obtained by the Investigator through review of these documents will be recorded and emailed to the Sponsor within 24 hours of receipt of the information. If a new SAE report form is emailed, then the Investigator must sign and date the form. The Sponsor may also request additional information on the SAE, which the Investigator or an authorized delegate must send via email to the Sponsor within 24 hours of the request.

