9.14. Follow-up visits

To follow-up on study patient visits 7 days (\pm 1 day) and 14 days (\pm 1 day) post-last dose are to be performed.

After arrival at the clinic patient identification is to be followed by alcohol test, urine drug screen and urine pregnancy test (for women). Vital signs measurements (respiratory rate, body temperature, 3-positional blood pressure and pulse) are to be performed, followed by 12-lead ECG. Afterwards blood and urine samples for clinical laboratory assessments are to be collected. Rating using ESRS and C-SSRS scales and also physical and neurological examinations are to be performed.

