4.8.1. Adverse event analysis

Any undesirable signs, symptoms or medical conditions occurring or worsening of pre-existing conditions between signing informed consent and the first administration of the study medication are considered as pre-treatment AEs. Undesirable signs, symptoms or medical conditions or worsening of pre-existing conditions occurring after the first administration of study medication are considered as treatment emergent adverse events (TEAEs).

A TEAE will be analyzed as related to study medication (i.e. as adverse drug reaction, ADR) if the relationship to study treatment was documented as 'unlikely', 'possible', 'probable', or 'definite' or if the relationship to study treatment is missing.

An overview table presenting the incidence of the following AE categories will be presented. Percentage of patients in each category will be compared between treatments as a difference in proportions between treatments including a 95% CI based on the Agresti – Caffo method (2000):

- All AEs
- Pre-treatment AEs
- Serious AEs (SAEs) (including pre-treatment SAEs)
- Treatment emergent AEs (TEAEs)
- Treatment emergent SAEs (TESAEs)
- Severe TEAEs
- Related TEAEs
- Related severe TEAEs
- TEAEs leading to reduction of dose
- TEAEs leading to interruption of dose
- TEAEs leading to permanent discontinuation (i.e. withdrawal) of study medication
- Related TEAEs leading to permanent discontinuation of study medication
- AEs leading to death (i.e. outcome of AE is fatal)
- TEAEs leading to death
- Related TEAEs leading to death

All treatment emergent AEs (TEAEs) and all serious TEAEs will be tabulated by MedDRA SOC and PT presenting the number and percentage of patients reporting the AE and the number of AEs reported. Additional tables will distinguish the events by whether the AE was related to study medication and by maximum severity.

All AEs documented in the eCRF will be listed by patient. Data listings will include patient ID, treatment group, verbatim term, preferred term, system organ class, start and stop date and relative day of the AE, severity, medications (yes/no), seriousness, action taken with study medication, relationship to study medication, and outcome will be provided. TEAEs will be flagged as such. In addition, separate listings for all SAE's, deaths and AEs leading to discontinuation (action taken with study treatment = drug withdrawn, or AE is reason for early termination) will be presented.

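### The protocol counts worsening of a pre-existing concomitant illness as an AE only on Days 1 to 28, a narrower window than its own AE collection period and the SAP's AE tables

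*Protocol*

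**What the plan says.** Protocol 8.3.1.1.1 has two neighbouring rules. The general one makes untoward events in the framework of the study AEs, and gives as an example "those occurring during treatment-free periods (including Screening or post-treatment follow-up periods"). The next paragraph is specific to concomitant illnesses that existed before entry: these "will not be considered AEs unless they worsen during the Treatment Period". Protocol 4.5 sets the Treatment Period as Days 1 to 28.

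Elsewhere the protocol uses a wider window. Section 8.3.1 has AE reporting run "from the date the informed consent form (ICF) is signed and will continue until the final Follow-up Visit". Section 8.3.1.2 has AEs recorded "from the date the ICF is signed until the end of their participation in the study".

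SAP 4.8.1 counts worsening of a pre-existing condition explicitly, on both sides of the first dose. Before it: "worsening of pre-existing conditions between signing informed consent and the first administration of the study medication are considered as pre-treatment AEs". After it, such worsening is a TEAE, and no end date is given. SAP 3.6 places the safety analysis after the follow-up visits are complete. SAP 3.4 records no change from the protocol.

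**The concern.** Read literally, the SAP plans to tabulate events that the protocol's specific rule tells sites are not AEs. An investigator who follows the specific sentence leaves out a comorbidity that worsens in washout or after the last dose. One who follows the general sentence records it. Both would be following the protocol, so recording may differ between sites.

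The two excluded stretches are ones where worsening can be foreseen. Under Protocol 5.4.3, antipsychotic and other psychotropic medication is stopped from the start of screening. After Day 28 the study drug itself is stopped. SAP 4.8.1 compares the percentage of patients with pre-treatment AEs, and with TEAEs, between treatments with 95% confidence intervals, so incomplete recording would pass into reported tables.

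**Working it through.** No sample size, power or event count enters this point. The check is a comparison of the passages and a count of days.

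**Which rule covers a non-serious worsening of a pre-existing concomitant illness?**

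| When it happens | Protocol 8.3.1.1.1, specific sentence | Protocol 8.3.1.1.1, general sentence | Protocol 8.3.1 and 8.3.1.2 | SAP 4.8.1 |
|---|---|---|---|---|
| Consent to first dose | Not an AE | AE, if the general rule prevails | Inside the window | Pre-treatment AE |
| Days 1 to 28 | AE | AE | Inside the window | TEAE |
| After the last dose, to final follow-up | Not an AE | AE, if the general rule prevails | Inside the window | TEAE (no end date; SAP 3.6 implies that follow-up is included) |

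The passages agree only in the middle row. The general sentence does not clearly settle the other two. It speaks of *other* untoward events, and the specific sentence follows it with its own limit.

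**How much time lies in those two rows?** Inputs, for a patient who uses the full schedule:

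- Screening including washout, Day -10 to Day -1 (Protocol 4.1, 4.5 and Table 1): 10 days.
- Randomization on Day 0 (Protocol 4.1, 9.3): 1 day.
- Treatment, Days 1 to 28: 28 days.
- Follow-up, Days 29 to 42: 14 days, or 13 to 15 with the ±1-day visit window.

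Collection window: 10 + 1 + 28 + 14 = 53 days.
Covered by the specific sentence: 28 / 53 = 53%.
Not covered: (10 + 1) + 14 = 25 days; 25 / 53 = 47%.
Not covered after first dose: 14 / 42 = 33%.

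The 25 days are a maximum. Screening is up to 10 days, and washout may be shorter or omitted in non-medicated patients.

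**What else would record such an event outside Days 1 to 28?**

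- Serious worsening: Protocol 8.3.1.1.2 defines an SAE without the restriction, and 8.3.1.4 states "All SAEs will be recorded from signing of the ICF until the final Follow-up Visit".
- Worsening that needs lorazepam, zolpidem, benzatropine/biperiden or propranolol: Protocol 5.4.3 requires the associated AE on the eCRF, and Table 5 covers the Screening Period. For pre-existing anxiety or insomnia that worsens in washout, 5.4.3 therefore expects an AE where the specific sentence says there is none.
- A clinically significant laboratory abnormality at the final Follow-up Visit: an AE under Protocol 8.3.2.

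What is left is non-serious worsening that needs none of those drugs and does not show as such a laboratory abnormality.

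**The case against.** The strongest reply is that this is one loosely worded sentence with little behind it. The paragraph before it already names screening and post-treatment follow-up, the routes listed above catch the more important events, and the same rule applies blind in every arm. Much of that stands. Events before first dose precede treatment and cannot create a drug effect in the TEAE comparison. After Day 28 the risk is undercounting, with no obvious direction between arms. What does not stand is that the general sentence cures the conflict: a site can reasonably follow the narrower rule that comes after it.

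Four stronger readings are tempting, and the documents do not support them.

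- A reader might infer that such worsening is never recorded. The other recording routes and the general sentence rule that out.
- A reader might infer that all 165 patients are affected because all have schizophrenia. The sentence concerns concomitant illnesses. Exclusion criterion 3 separates other disease from the disease under study, and 8.3.1.1.1 treats lack of efficacy in its own sentence. Whether schizophrenia is covered is unclear.
- A reader might infer that an AE record is the only place where worsening of psychosis outside the Treatment Period could appear. PANSS and CGI-S are rated at Screening and Day -1. Follow-up has no PANSS or CGI, but Protocol 9.14 states "Rating using ESRS and C-SSRS scales and also physical and neurological examinations are to be performed", and the physical examination in 8.3.6 includes the psychiatric system. Patients may also resume antipsychotics from Day 29, which complicates any reading of follow-up events as rebound.
- A reader might infer that washout worsening is the reference for judging treatment-emergent worsening. SAP 4.1.1 takes baselines from Day -1 or Day 1, and SAP 4.8.1 compares AE incidence between treatment groups.

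**Conclusion.** The conflict is in the current text and should be reconciled. Its consequence is limited: non-serious worsening of a pre-existing concomitant illness, up to 11 days before first dose or about 14 days after the last, may be missed or recorded inconsistently between sites. The pre-treatment AE counts and the post-Day-28 part of the TEAE counts may therefore be incomplete.

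The 47% is the largest share of calendar time outside the sentence. It is not a share of events or of data lost, and the documents give no figure for how many patients would have such worsening. The conclusion assumes that at least some sites follow the specific sentence over the general one, and that the SAP's open-ended TEAE definition extends through follow-up, as SAP 3.6 implies. No efficacy analysis is affected. Severity: minor.

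**What to change.** In Protocol 8.3.1.1.1, replace the Treatment Period limit with the collection window of 8.3.1, from signature of the ICF to the final Follow-up Visit. In the same place, state whether the sentence covers worsening of schizophrenia itself. SAP 4.8.1 can then classify each event as pre-treatment or treatment-emergent without changing its definitions.

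Where sites have already applied the narrow rule, query screening, washout and follow-up worsening before the safety database is locked. If that is not possible, disclose the limitation in the CSR.

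The cost is one phrase and one clarifying statement in the protocol, a site memo and some queries. AE counts may rise slightly in all arms.
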